1.0 PROTOCOL SUMMARY AND/OR SCHEMA

This is an open observational study being done to test the feasibility and reproducibility of a hyperspectral camera system (HCS) in human skin perfusion. Oxygenation detection will be evaluated, resulting in selection of spectral bands, which could be used in clinical practice. Eight healthy volunteers will be included.

Feasibility and reproducibility of a hyperspectral camera system in human skin perfusion and oxygenation detection will be evaluated, resulting in selection of spectral bands, which could be used in clinical practice.

2.0 OBJECTIVES AND SCIENTIFIC AIMS

Primary Objective:

To investigate the feasibility, applicability, and reproducibility of a novel hyperspectral camera system in perfusion and oxygenation detection in healthy volunteers.

Secondary Objectives:

- To explore the effect of occlusion-reperfusion of the brachial artery on cutaneous blood flow as assessed by a hyperspectral camera system.
- To explore the effect of applying topical vasoconstrictors / vasodilators on the cutaneous blood flow as assessed by a hyperspectral camera system.
- Selection of relevant spectral bands for oxygenation and perfusion detection.

3.0 BACKGROUND AND RATIONALE

Restoring normal functioning and tissue healing after surgical intervention is, among others, critically dependent on tissue perfusion. Insufficient perfusion with oxygenated blood could result in ischemia and subsequent tissue damage. An important clinical problem is anastomotic leakage, which is one of the most serious complication after gastrointestinal surgery. Anastomotic leakage has a prevalence varying between 1 and 19% and a mortality of 6 to 22% in patients with colorectal cancer [1-5]. Hence, adequate bowel anastomosis is important to prevent leakage. As tissue perfusion is one of the most important risk factors for anastomotic leakage it appears that assessment of perfusion, particularly upon establishment of the anastomosis during surgery, can contribute to better surgical outcomes.

Currently, evaluation of tissue perfusion during surgery can be performed with NIR fluorescence imaging by intravascular injecting indocyanine green (ICG) as fluorophore. Several clinical trials showed good results in evaluating the perfusion of bowel anastomoses and skin flaps used for reconstructive surgery [6-8]. Other optical

techniques, which do not require administration of contrast agents, have also been used to evaluate tissue perfusion and oxygenation. Optical coherence tomography showed the capability to detect in vivo oxygen saturation levels by using the optical absorption coefficient differences between oxygenated and deoxygenated haemoglobin [9]. Laser Doppler imaging can also be used to measure blood flow, but lacks resolution to assess flow in individual vessels [10]. Laser speckle imaging is able to detect individual moving particles such as blood cells. The movement these cells are related to the blood flow velocity, which can be displayed in real-time. Hence, the technique can be used for blood perfusion mapping.

An emerging technique is hyperspectral imaging, which is capable to detect the scattering and absorption of light delivered to the tissue, caused by inhomogeneity of biological structures, such as haemoglobin, fat or water [11]. In vivo real-time imaging of the perfusion is currently not possible, however snapshot imaging was used to evaluate oxygen levels in the retina, which was quite complex, especially the part of data processing [12, 13]. Recently, a novel hyperspectral imaging camera (Quest Medical Imaging BV, Middenmeer, The Netherlands) has become available as prototype. This device allows non-invasive measurement of skin blood flow, oximetry and (vascular) anatomy, only based on the endogenous contrast of the tissue. Therefore it could be used to obtain non-invasively information about the (superficial) anatomical structures and moreover to measure the microvascular condition.

However the capability of this device to pick up physiological changes is unknown. To validate this hyperspectral camera system (HCS) for measuring skin blood flow and vascular anatomy the following study is proposed:

- Measurement of forearm skin blood flow before, during and after occlusion of the brachial artery;
- Measurement of local changes in skin blood flow after applying a local capsaicin-based cream (local vasodilator);

Read outs from the HCS after local application of capsaicin-based cream will be compared to measurements of an untreated area of the forearm. Furthermore, the changes in these measurements will be evaluated over time..

Hyperspectral camera system:

Hyperspectral imaging is a non-invasive optical technique, using halogen light as a light source, which is also widely used in commercially available light sources. Halogen light could produce some heat, however imaging will be performed on a distance of 50 centimetres. The technology used in this camera, is partially comparable to the technology used in Diffuse Reflectance Spectroscopy, which has been used in diverse clinical studies in the Netherlands Cancer Institute without reporting of any side effects during the measurements [17, 18].

Summary of findings from non-clinical studies

The HCS is recently developed and is one of the first camera systems which is expected to create two-dimensional imaging of tissue perfusion based on endogenous tissue contrast, which is far beyond the current state of the art. This study will be the first clinical study in human volunteers and no findings of earlier performed non-clinical studies are available.

We expect no side effects, because this technique only uses halogen light as light source, which is also widely used in commercially available light sources. The sensors used in this camera, are partially comparable to the sensors used in Diffuse Reflectance Spectroscopy. In the Netherlands Cancer Institute good results in tissue characterization and tumor detection were achieved, however this technique is only capable to perform point measurements and could therefore not be used during surgery in the future. They also showed that no side effects occurred during and after the measurements [17, 18].

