4.0 OVERVIEW OF STUDY DESIGN/INTERVENTION

4.1 Design

This study is a non-therapeutic open observational trial, which evaluates the feasibility of the hyperspectral camera system (a non-significant risk device) in evaluation of the tissue perfusion and oxygenation in different circumstances. The exploratory aim of this study is to select relevant spectral bands for oxygenation and perfusion detection, which can be used for further camera development and consequently in clinical practice. Eight healthy volunteers, without any medication use and without any relevant medical history will be included in this study. Subjects will be enrolled following confirmation of study eligibility (section 5.0) which will be checked at baseline. Reproducibility will be validated by performing the following HCS measures:

- Basal blood flow
- Blood flow upon occlusion-reperfusion brachial artery
- Blood flow after applying capsaicin-based cream
- The room temperature, which could influence the skin perfusion will also be measured.

For the secondary endpoints, hyperspectral measures of:

- basal blood flow / oximetry
- blood flow /oximetry upon occlusion-reperfusion brachial artery
- Blood flow / oximetry after applying capsaicin-based cream

Reproducibility will be validated by the HCS measure only, at both time points that the HCS is used.

Explorative endpoint:

The explorative endpoint of the study is to see if a selection of spectral bands, specific for tissue perfusion and oxygenation (selected after data processing of above mentioned measurements) can be achieved.

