7.0 ASSESSMENT/EVALUATION PLAN

Subjects will participate on 2 similar study days, separated by a minimum of 3 days and maximal 28 days. Measurements will be assessed by the HCS and will take maximum 2 hours.

Pre-treatment evaluation (after study consent and registration of volunteers):

- Medical history review
- Weight

Once eligibility is confirmed:

- Blood pressure
- Heart rate
- Room temperature

On study procedures to be followed:

- 1) The volunteer is installed at the test location (Pre-surgical Center, M-6) at the main hospital

- 2) Before starting the measurements, the blood pressure, heart rate and room temperature are measured to establish the baseline characteristics.
- 3) The volunteer is asked to stretch both forearms near to each other in sitting position.
- 4) The blood flow is measured by the HCS at baseline on both forearms (Total field of view: max. 10 x 10 cm)
- 5) After baseline measurements the flow is measured on either the right or left forearm during five minutes occlusion (a blood pressure cuff will be used) of the right brachial artery and during five minutes of reperfusion after occlusion.
- 6) After taking these measurements, there is a short break of 5 minutes, to save all measurements.
- 7) Local capsaicin-based cream is administrated on the same forearm on an area of 3 x 3 cm, on a distance of 5 cm under the radiocarpal joint.
- 8) 30 minutes after application of the crème, crème is removed from the skin.
- 9) For obtaining optimal flare, 20 minutes after removing the crème, the perfusion is measured by HCS for 5 minutes.
- 10) Region with administrated local capsaicin-based cream is compared to control regions located on the same forearm,
- 11) After 10 minutes the procedure is finished.

Concomitant medications and alcohol/caffeine consumption

The use of the following concomitant medications is prohibited: no prescription medications, over-the-counter (OTC) medications, vitamin, herbal and dietary supplements will be permitted within 14 days prior to study drug administrations, or less than 5 half-lives (whichever is longer, and during the course of the study. The following exceptions are applied:

- paracetamol (up to 4 g/day).
- Other exceptions will only be made if the rationale is discussed and clearly documented by the investigator

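### Section 3.0 promises validation for skin blood flow and vascular anatomy, but with no independent reference and no anatomy outcome the plan can support only repeatability and responsiveness

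*Combined protocol and SAP*

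**What the plan says.** The claim is in Section 3.0: "To validate this hyperspectral camera system (HCS) for measuring skin blood flow and vascular anatomy the following study is proposed". What follows it is two challenges: occlusion of the brachial artery, and a capsaicin cream compared with untreated forearm skin.

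The same section describes the technique as "capable to detect the scattering and absorption of light delivered to the tissue". It then says "This device allows non-invasive measurement of skin blood flow, oximetry and (vascular) anatomy, only based on the endogenous contrast of the tissue", and soon after: "However the capability of this device to pick up physiological changes is unknown". It adds that "no findings of earlier performed non-clinical studies are available".

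Section 4.1 lists the camera outputs as blood flow and oximetry, and says: "Reproducibility will be validated by the HCS measure only, at both time points that the HCS is used". Section 7.0 says: "Measurements will be assessed by the HCS and will take maximum 2 hours"; the only other study-day measurements are blood pressure, heart rate and room temperature.

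The primary objective in Section 2.0 concerns whether the camera is feasible, applicable and reproducible. Section 11.0 plans t-tests on camera perfusion and room temperature and an intra-subject CV over the two days, with no acceptance limit. It plans no statistical analysis of the spectral measurements.

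**The concern.** Validating a device for blood flow means showing that its read-out agrees with, or at least specifically follows, blood flow. By the protocol's own account the camera senses light absorbed and scattered by tissue. The processing steps in Section 4.2 (denoising, merging, feature extraction, principal components) give no conversion from spectrum to flow. The labels blood flow and oximetry are therefore assumed at the outset, although the device's response to physiology is stated to be unknown.

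What is at stake is interpretation. Sections 3.0 and 4.1 look ahead to surgical and clinical use. If a repeatable, responsive signal is carried forward as a validated flow measurement, later work will rest on a property that this study did not examine. For vascular anatomy the gap is complete, because nothing is planned that could support the claim.

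**Working it through.** **1. Tracing the claim through the protocol**

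| Section | Non-camera flow or oxygenation measure | Anatomy outcome |
|---|---|---|
| 2.0 Objectives | none | none |
| 4.1 Design, endpoints | none | none |
| 7.0 Procedures | none | none |
| 9.0 Assessment table | none | none |
| 11.0 Biostatistics | none | none |

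Laser Doppler and laser speckle appear only as background in Section 3.0. The colour image in Section 4.2 serves annotation.

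**2. Does the primary analysis depend on tracking flow?**

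From the documents: 8 volunteers, 2 days. They give no alpha, power, SD or CV target, so there is no figure of the plan's own to reproduce. Assumed here: a paired t-test at two-sided 0.05, mean read-out 100, between-subject SD 10, within-subject SD 5, and a true flow level F that is stable for each subject.

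Model: y(i,day) = 100 + 10·U(i) + 5·e(i,day), with U = rho·F + sqrt(1 − rho²)·Z. F, Z and e are independent standard normal, and rho is the correlation of the stable part of the read-out with flow.

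- Between-day difference: d(i) = 5·[e(i,1) − e(i,2)]. U cancels, so the paired t-test does not contain rho.
- Subject CV = |d(i)| / (sqrt(2)·subject mean), combined over subjects as a root mean square. U enters only through the subject mean, and U is standard normal whatever rho is. The CV therefore has the same distribution for every rho.

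Simulation, 20,000 runs (correlation column from 3,000 of them):

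| rho | t-test non-significant | Median CV | Median correlation of two-day mean with flow |
|---|---|---|---|
| 0 | 95.0% | 4.9% | 0.00 |
| 0.5 | 95.1% | 4.9% | 0.50 |
| 0.95 | 95.1% | 4.9% | 0.91 |

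The 4.9% follows from the assumed 5/100. That it is the same in each row does not depend on the SDs chosen. If flow really differed between days, a read-out that followed it would show the larger CV, so a low CV is not evidence of tracking.

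**3. What the challenges can show**

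A read-out fixed by static skin properties should not change under occlusion, reperfusion or capsaicin, so the challenges can expose it. A read-out driven by haemoglobin content or by oxygenation could change under them, as could one driven by flow. Nothing in the documents rules this out, and Section 3.0 names haemoglobin as a source of the signal. A response is therefore evidence of responsiveness and does not identify flow.

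Section 11.0 names no contrast of baseline with occlusion or reperfusion, and none of capsaicin with control skin. In addition, Section 7.0 (step 5) and the second footnote in Section 9.0 allow either forearm to be imaged while the occluded artery is always the right one. If the left arm is imaged, the occlusion is not in view.

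**4. What eight volunteers can deliver**

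- Mean within-subject change, 95% half-width: t(0.975; 7)/sqrt(8) = 2.365/2.828 = 0.84 SD of the changes.
- Paired t-test, 80% power: a mean difference of about 1.16 SD of the differences.
- Within-subject SD, 95% CI (8 df): 0.68 to 1.92 times the estimate, from sqrt(8/chi-square quantile).
- If a reference device were added, one value per subject, tanh[atanh(r) ± 1.96/sqrt(5)]: r = 0.7 gives −0.01 to 0.94; r = 0.9 gives 0.53 to 0.98. Each limit of agreement would have a half-width of 2.365·sqrt(1/8 + 1.96²/14) = 1.49 SD of the differences.

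A reference at this sample size would give pilot-level information only, so narrowing the claim is the proportionate remedy.

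**The case against.** The strongest reply is that this is an eight-person feasibility study whose formal objectives do not promise accuracy, and that one sentence of rationale is being read too hard. That sentence introduces physiological challenges with a control area, and Section 4.2 argues from whether the camera detects the induced changes, not from the CV. Much of this stands, and it rules out several stronger readings that a reader might infer:

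- *A low CV would pass as validated flow.* The plan sets no CV limit and nowhere says that repeatability proves validity.
- *The design cannot tell flow from static skin reflectance.* A purely static read-out would fail the challenges. What they leave unresolved is flow against haemoglobin content or oxygenation.
- *"Reproducibility will be validated by the HCS measure only, at both time points that the HCS is used" concedes that accuracy goes unchecked.* It describes the test-retest comparison, for which using one device is normal. The absence of a reference is shown by the procedures and assessments.
- *The validation claim runs through the protocol.* The wording on flow and anatomy is in Section 3.0 only. Section 4.1 speaks of validating reproducibility.

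The user manual and the protocol of the collaborating Leiden centre are listed as appendices but are not available here, and that centre's data will be pooled. A reference measure there cannot be excluded; this protocol describes none.

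The reply does not remove the mismatch. Section 3.0 announces a property for which the objectives, procedures and analysis make no provision, and the challenges that come closest to it have no specified analysis.

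**Conclusion.** The point holds as a mismatch between the claim and the design. As described, the study can estimate the repeatability of camera-derived indices and can show whether they respond to two challenges. It cannot establish that they measure blood flow, and it contains nothing on vascular anatomy.

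The mismatch has no numerical bias to report. Its size is that the planned t-test and CV carry no information on tracking of flow: results were the same at a correlation of 0 and of 0.95. The 4.9% and 95% figures rest on the assumed mean, SDs, paired test and stable flow; their equality across correlations does not rest on the SDs. That the challenges do not isolate flow rests on the camera sensing absorption and scattering with no stated conversion to flow.

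This should be corrected before results are written up. It does not prevent the study from meeting its Section 2.0 objectives.

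**What to change.** - **Section 3.0:** replace the validation wording with a statement that the study describes the repeatability and responsiveness of HCS-derived perfusion and oxygenation indices. Delete vascular anatomy from the claim.
- **Sections 2.0 and 4.1:** label the outputs as HCS-derived indices, not as established blood flow or oximetry.
- **Section 11.0:** add a within-subject responsiveness analysis of recordings already planned: baseline against late occlusion against reperfusion, and capsaicin-treated skin against the same-forearm control area. Define the time windows and regions beforehand, keep the volunteer as the unit, and report estimates with 95% CIs beside the between-day CV. State that neither repeatability nor responsiveness alone supports a claim of validated flow.
- **Sections 7.0 and 9.0:** reconcile the imaged forearm with the occluded artery so that the imaged arm is known to be the occluded one.
- **Appendices:** if the Leiden protocol includes a reference measure, say so in Section 11.0 and state how it will be used.

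A rule that awards the label flow to any read-out that falls during occlusion and overshoots on release would not be a safe substitute, because an oxygenation signal could do the same.

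Cost: wording changes, a small extra analysis and a narrower claim. No added volunteers, visits or equipment are needed.

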After each measurement of a specific tissue part, a 3-dimensional hypercube with a corresponding graph could be created after data processing as illustrated in this figure [11].

The HCS consists of three sensors, creating three images, that have to be merged to a 3D datacube. Before merging, the images has to be analysed. In general, hyperspectral image analysis will consist of preprocessing, feature extraction and selection, and classification. Noise could be removed by preprocessing part of data analysis by diverse denoising techniques. After denoising, the images could be merged to a 3D datacube. Afterwards, feature extraction will be applied to select clinically relevant spectral bands for perfusion and oxygenation measurements. Finally, principle component analysis is used to reduce redundant information in the bands of hyperspectral imagery while preserving as much of the variance in the high dimensional space as possible [11].

Non-Investigational products:

1. Capsaicin crème FNA 0,75 mg/g Capsaicin-based cream is a selective 'transient receptor potential vanilloid 1-receptor' (TRPV1) agonist. It is registered for use in the treatment of local itch, post herpes neuralgia or diabetic polyneuropathy. The compound has been selected because of it induces release of vasoactive neuropeptides causing vasodilatation.

The medication will be administrated cutaneously, according to the prescription. We will use the commonly used concentration of cream for clinical practice.

The cream will be administrated cutaneously. Capsaicin cream we will use a 0.075% dosage.

The cream will only be used during this feasibility study to induce vascular changes in healthy human volunteers. The cream will be supplied by the MSK pharmacy as per standard single patient ordering procedures. We aim to detect these small vascular changes with the hyperspectral camera. If the camera is able to detect these changes, it has the potential to detect small vascular changes in patients with bad vascular perfusion for whatever reason (vascular diseases, surgical intervention etc.). We will emphasize that the medication is not necessary for using the hyperspectral camera, however it is only used to induce vascular changes.

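### No control region is specified to receive cream base or cream removal, so the capsaicin contrast cannot be attributed to vasodilation alone

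*Combined protocol and SAP*

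**What the plan says.** The cream is one of two manoeuvres that Section 3.0 proposes for validating the camera; the other is brachial occlusion and reperfusion. Section 2.0 makes the effect of topical vasoactive agents a secondary, exploratory objective.

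- **Comparator.** Section 3.0: "Read outs from the HCS after local application of capsaicin-based cream will be compared to measurements of an untreated area of the forearm". Section 7.0 step 10: "Region with administrated local capsaicin-based cream is compared to control regions located on the same forearm".
- **Treated site.** Step 7: "Local capsaicin-based cream is administrated on the same forearm on an area of 3 x 3 cm". Step 8: "30 minutes after application of the crème, crème is removed from the skin". The method of removal is not described and no check for residue is planned.
- **Timing.** Step 9: "For obtaining optimal flare, 20 minutes after removing the crème, the perfusion is measured by HCS for 5 minutes".
- **Pre-cream image.** Step 4: "The blood flow is measured by the HCS at baseline on both forearms".
- **What the technique senses.** Section 3.0 describes scattering and absorption of light "caused by inhomogeneity of biological structures, such as haemoglobin, fat or water".
- **Inference intended.** Section 4.2: "If the camera is able to detect these changes, it has the potential to detect small vascular changes in patients with bad vascular perfusion".

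Capsaicin cream is the only product applied. No base cream, placebo cream or sham-cleaned region appears in the documents.

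**The concern.** The inference in Section 4.2 runs from a detected change at the cream site to an ability to detect vascular change. It needs a contrast in which only vascular state differs. Here the treated site differs from its comparator in three specified respects at once: capsaicin, contact with a base, and removal. The imaging technique is described as sensitive to fat and water, and a cream can leave or change both at the skin surface. A difference between sites might therefore be partly optical or mechanical. Equally, a real capsaicin response might be hidden if the other effects pull the read-out the opposite way.

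Two uses of the data are exposed: the exploratory conclusion about the topical vasodilator, and the choice of spectral bands. Section 4.1 draws the bands from all the measurements, including the cream images, and intends them for further camera development.

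**Working it through.** The plan gives no figure for this contrast, so there is nothing to reproduce. The check sets the passages side by side and follows what each comparison can isolate.

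**1. What each region is specified to receive (Section 7.0, steps 7 to 10)**

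| | Capsaicin | Base, 30 min | Removal |
|---|---|---|---|
| Treated 3 x 3 cm patch | yes | yes | yes |
| Control regions | no | not specified | not specified |

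Section 3.0 calls the comparator untreated.

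**2. What the contrasts estimate**

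Let T and C be the treated and control read-outs, with 0 before cream and 1 after. Let c be the capsaicin effect, b the effect of base contact (residue, hydration), w the effect of removal (rubbing), and s a fixed site difference. Each may be positive or negative. Assume that they add and that drift over time is common to both sites.

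- Post-cream contrast: T1 − C1 = s + c + b + w.
- Change from baseline, if the same regions can be located in the step 4 images: (T1 − T0) − (C1 − C0) = c + b + w. The baseline removes s but leaves b and w, which arise later and only at the treated site.
- Repeat visit: the Section 9.0 table has cream at both visits, so a constant b + w recurs. The between-visit coefficient of variation in Section 11.0 would not reveal it.
- Control cleaned in the same way: change contrast = c + b.
- Control given base and cleaned in the same way: change contrast = c.

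Only the last isolates capsaicin; the one before it removes the rubbing term.

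**3. Illustration on assumed inputs**

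Section 11.0 names no treated-versus-control test, alpha or standard deviation. Assume a two-sided paired t-test with n = 8 (Section 1.0) and alpha 0.05, so the critical value on 7 degrees of freedom is 2.365. Express the net shift as d standard deviations of the within-subject difference. The noncentrality is d × √8. With c = 0 and d made up of b + w only:

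| d (either sign) | d × √8 | Probability of a significant result |
|---|---|---|
| 0 | 0 | 0.05 |
| 0.25 | 0.71 | 0.094 |
| 0.5 | 1.41 | 0.232 |
| 1.0 | 2.83 | 0.681 |
| 1.5 | 4.24 | 0.951 |

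The same table shows masking. If c = +1.0 and b + w = −0.5, the net shift is 0.5 and the probability of detection falls from 0.681 to 0.232. These rows show how the answer depends on an unknown; they do not estimate it.

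**The case against.** Several points on the other side stand.

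- **The artefact is plausible, not shown.** The sentence on haemoglobin, fat and water describes hyperspectral imaging of tissue in general. Nothing in the documents says that this camera responds to residue or hydration 20 minutes after removal. The wait is justified by flare, but it may let a rubbing effect fade. The co-registered colour image (Section 4.2) might also show gross residue.
- **The stakes are modest.** The cream aim is secondary and exploratory, eight volunteers are planned, and Section 4.2 speaks only of potential.
- **Cost is not nil.** No document says that a matching base exists. Section 11.0 plans to pool with data from Leiden University Medical Center (LUMC), collected under a separate but similar protocol whose text is not available here.

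Three stronger readings are tempting and not supported.

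- A reader might infer that the control skin is left untouched. The text says untreated; whether control regions are wiped is simply not stated.
- A reader might infer that a camera blind to perfusion would still pass validation. The occlusion-reperfusion images involve no cream, and such a camera should show no response there. The plan does not require that cross-check, but it collects the data for it.
- A reader might want to state what share of the cream signal is artefact. Any such percentage restates an assumed ratio and presumes effects in the same direction, which the documents do not establish.

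None of this separates capsaicin from base and removal within the cream contrast. Occlusion is a different stimulus: it can show that the camera sees perfusion, not what produced the signal at the cream site.

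**Conclusion.** The point holds as a limit on attribution. As specified, the cream contrast estimates the combined effect of capsaicin, base and removal, and neither the pre-cream image nor the second visit separates them. Size and direction are unknown from the documents. On the assumed test, a non-capsaicin shift of 0.25 to 1.5 standard deviations would give a significant result with probability 0.094 to 0.951 when capsaicin had no effect, and a shift of opposite sign could hide a true effect. This rests on additive effects and on control regions receiving neither base nor removal, which is how the procedure reads but is not stated outright.

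The occlusion-reperfusion results are unaffected. No stated error rate is breached, because none is stated. This is a worthwhile, inexpensive improvement to an exploratory component, best made before imaging, since a control that was not imaged cannot be recovered.

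**What to change.** 1. In Section 7.0 steps 7 to 10, name one control region and clean it in the same way and at the same moment as the cream is removed from the treated patch. Describe the method of removal.
2. Where the pharmacy can supply a matching capsaicin-free base, apply it to that region at step 7, over the same 3 x 3 cm and for the same 30 minutes, clear of the capsaicin site and its flare.
3. Make this region the main cream comparator and keep an untreated region as a second control. With cleaning alone, report that a base effect has not been excluded.
4. In Section 4.2, require that any perfusion band chosen from the cream images also responds to occlusion-reperfusion. This presupposes that the imaged forearm is the occluded one; step 5 allows either forearm to be imaged while the right artery is occluded, and that wording needs reconciling.

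**Cost.** A protocol amendment, and sourcing of a base. No visit time is added, because the extra steps run in parallel: steps 5 to 11 already take 5 + 5 + 5 + 30 + 20 + 5 + 10 = 80 minutes of the 2-hour maximum. Layout needs planning: three 3 cm regions in a line take 9 of the 10 cm field of view, leaving 1 cm for gaps, so they may need to be staggered or imaged in two frames. The LUMC procedure should be aligned; otherwise its cream data should be analysed separately rather than pooled.
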